## **COST-UTILITY**

In the same manner, if the main medico-economic evaluation reveals a statistically significant study group difference, in a given country, a cost-utility evaluation will be performed, in the same way as the cost-effectiveness evaluation, the denominator of the calculated ICERs being in that case, the difference in QALYs (*as defined in section 6.C.3*).

### 7.B.3.7. Evaluation of safety

Safety data will be tabulated descriptively by study group (*and globally*) and assessment time, when relevant. Whenever applicable, they will be tabulated twice: first, during the *Run-In Period* on the FAS (*defined in section 7.B.3.1*) and second, during the *Follow-Up Period* on the ITT data set (*defined in section 7.B.3.1*). No statistical test will be performed.

## **EXTENT OF EXPOSURE**

Duration of the *Run-In Period*, duration of the *Follow-Up Period* and overall study duration will be tabulated (*expressed in months, rounded at one digit*) by study group (*and globally*), as both quantitative and categorical data.

Overall study duration is defined as the time interval between the actual date of Selection (*included*) and the actual date of the last visit (*or phone contact*) performed by the investigator (*visit planned to be performed at the time of premature withdrawal or on theoretical visit date corresponding to Month 24 (for the first patients included in the study) or Month 12 (for the patients included afterwards)*) (*excluded*), *i.e., as the quantity “date of last visit performed by the investigator - date of Selection”*.

Cumulative individual number of days on oxygen therapy will be tabulated (*expressed in months, rounded at one digit*) by study group (*and globally*), as both quantitative and categorical data. It will be calculated taking into account the individual start date of each oxygen prescription and its corresponding end date, if applicable, for each oxygen prescription overlapping the overall study duration previously defined. If a given patient starts his/her oxygen therapy after his/her date of Selection in the study and if he/she ends it definitively before his/her last study visit, his/her individual number of days on oxygen therapy will be calculated as “end date of the oxygen prescription – start date of the oxygen prescription + 1 day”. For patients who were never prescribed oxygen therapy throughout their whole study participation, the individual number of days on oxygen therapy will be described as equal to 0 days.

## **ADVERSE EVENTS**

Any adverse event (*either serious or not serious, according to their regulatory definition provided in section 8.A*) having been reported throughout the study for a given patient will be classified by preferred term and corresponding System Organ Class, using the MedDRA terminology, prior to the database lock.

Any Adverse Event (AE) reported after Visit 1 will be considered Study Emergent (SE):

- i)* if it begins after Visit 1 date,
- or *ii)* if its start date is unknown,
- or *iii)* if it begins before Visit 1 and worsens at any time during the *Follow-Up Period*.

If applicable, any AE starting before Visit 1 and going on afterwards will be considered study emergent if its severity is missing or partially filled in. In the same manner, any AE starting before Visit 1 with missing or incomplete end date will be considered study emergent. If the same AE occurs twice in a given patient, once with onset and end dates during the *Run-In Period* and once during the *Follow-Up Period*, it will be described twice, as both an AE occurring before Visit 1 and a SE AE.

The time period for the assessments of AEs is the time interval between Selection (*Visit 0*) and Study End (*Visit 9 for the first patients included in the study or Visit 5 for the patients included afterwards*), divided in two (2) successive periods: the *Run-In Period* and the *Follow-Up Period*.

All reported AEs will be classified in these two (2) periods, according to their start date. AEs reported during the *Run-In Period* will be tabulated on the FAS and on the ITT data set separately, as described below, if relevant or they will only be listed if too few patients are concerned.

The number and percentage of patients having experienced at least once a given SE AE during the *Follow-Up Period* will be tabulated by study group (*and globally*), System Organ Class and preferred term. Tabulations will include:

- the number and percentage of patients having experienced at least once a given SE AE,
- the number and percentage of patients having experienced at least once most common SE AEs (*defined as those occurring in at least 5.0% of the patients from the ITT data set*), if it appears to be relevant,
- the number and percentage of patients having experienced at least once a given SE AE, by most severe intensity,
- the number and percentage of patients having experienced at least once a given SE AE, by most severe relationship to the allocated study intervention.

The number and percentage of patients having experienced at least once a given SE AE during the *Follow-Up Period* will also be tabulated by study group (*and globally*) and System Organ Class only.

Over both study periods, separately and globally, an additional summary table will be provided by study group (*and globally*), including:

- the number and percentage of patients having experienced at least one SE AE,
- the number and percentage of patients having experienced at least one study intervention associated SE AE (*study intervention associated SE AEs being defined as SE AEs for which the investigator has reported at least once relationship to the allocated study intervention, either not excluded or unassessable*),
- the number and percentage of patients having experienced at least one AE leading to premature discontinuation of the allocated management strategy,
- the number and percentage of patients having experienced at least one AE leading to study premature withdrawal.

Moreover, over both study periods, separately and globally, a summary table will be provided by study group (*and globally*), including:

- the total number of SE AEs reported,
- and the distribution of the number of SE AEs reported by patient (*by 5-event categories: [1 ; 5], [6 ; 10], [11 ; 15], ...*).

Both summary tables will also be provided for Serious Adverse Events (SAEs), over both study periods, separately and globally. If relevant, the number and percentage of patients having experienced at least once a given SAE will also be tabulated by study group (*and globally*), System Organ Class and preferred term, separately from all AEs, in a second step, to retrieve them more easily.

For the whole evaluation of AEs (*including the counting of the number of AEs reported*), recurring AEs (*i.e., AEs classified with the same preferred term*) for a given patient in a given period will only be counted once for the concerned patient in the concerned period.

All SAEs reported throughout the study, from the date of Selection onwards, will be listed and exhaustively described on an individual basis, by study group, including all reported information on the AEs specific e-CRF, as well as their start date (*i.e., the time interval between the date of Visit 0 and the occurrence of SAEs*), period of occurrence and duration.

All AEs leading to premature discontinuation of the allocated management strategy, as well as all AEs leading to study premature withdrawal (*both of these AEs constituting significant AEs*) will be listed and exhaustively described, on an individual basis, by study group, in exactly the same way as SAEs, throughout the study.

Results of ECG and physical examination will not be tabulated or listed, as any new abnormal findings diagnosed after the *Run-In Period* should be reported as AEs (*if clinically significant*).

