## 1.B RATIONALE

The goal of the study is to evaluate a Home-Based Disease Management program specifically adapted for patients with GOLD III/IV COPD. Acute episodes requiring hospitalisation are more frequent in these patients with severely compromised lung function. Additionally, they are major contributors to health status decline and health costs. Therefore, the study primary objective is to show a significant reduction in the number of hospital days during the 12-month study follow-up in patients receiving the study program as compared to patients receiving usual care.

Key interventions of the study program combine four components of chronic care: *i) patient education, ii) patient motivation (to promote self-efficacy and self-management), iii) closer patient follow-up to allow early detection of significant clinical worsening, and iv) coordination of health care to reduce time to treatment.*

During the study, **patients of the Intervention group will receive an educational program provided by community-based health professionals** individually at home, in group sessions, and by telephone. The study educational program was adapted from the original 'Living Well With COPD' program, initiated, evaluated and implemented in Canada by the Montreal Chest Institute of the McGill University Health Centre since 1998. This program has been shown to have a sustained positive impact on patient's health, on health-related quality of life, and on the use of acute hospital care, resulting in significant cost of care savings. The program contains disease knowledge education because it is essential for patients with COPD to understand their disease, risk factors for its progression, and objectives of their medication in order to promote compliance to therapeutics, including oxygen therapy, and to encourage "healthy behaviours" such as smoking cessation and regular physical activity. The program also contains a patient-tailored 'action plan' that includes teaching of techniques to self-perform home respiratory assessments, and specifying the steps to follow in particular situations, such as acute worsening of respiratory symptoms, so as to reinforce the patient's role in achieving better disease control.

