### 3.A NUMBER OF PATIENTS / ENROLMENT/ FOLLOW-UP PERIOD

This study will include a total of 306 patients (*153 in each group, see section 7.B.2*), randomly assigned to one of the two study groups detailed in section 4.A by centre, smoking status and need for respiratory assistance (*i.e., home oxygen therapy or Non-Invasive Ventilation*) for chronic respiratory failure at Selection.

The planned total study duration is 52 months, including a 38-month enrolment period and a 14-month follow-up for each randomised patient.

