#### 4.B.3.2. Follow-Up Period

The *Follow-Up Period* starts at the end of Visit 1 and will last 12 months for each patient.

Patients will undergo during this period:

- **Visits** at the investigational centre every 3 months (*Visits 2 to 5*),
- **Standardised phone interviews** performed by an investigational centre staff member every 3 months between the patient visits at the investigational centre (*Centre phone contacts 1 to 4*),
- And, **for patients randomised in the Intervention group**, education sessions given by a health counsellor every month (*alternatively group and phone sessions*), and an at least weekly prospective telephone follow-up while **for patients randomised in the Control group**, the usual COPD education and follow-up as per investigational centre routine practice.

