## **VISITS AT THE INVESTIGATIONAL CENTRE (*VISITS 2 TO 5*)**

**Visits 2 to 5** are scheduled at Month 3, Month 6, Month 9 and Month 12 from Visit 1, respectively. These visits may vary from their planned timelines starting at Visit 1 by  $\pm 30$  days, without modifying the initially planned timelines of the following visits if a given visit needs to be advanced or postponed.

**During Visits 2 to 5**, the investigator will record the following data in the e-CRF:

- Date of Visit,
- Results of the physical examination including vital signs (*i.e.*, *systolic and diastolic blood pressures*), weight and pulse oximetry (*pulse rate and SpO2*) on room air and also on oxygen for patients on oxygen therapy,
- Changes in social conditions, if applicable,
- Changes in smoking status, if applicable,
- Recovery from concomitant diseases since the last visit, if applicable,
- Changes in COPD and non-COPD medication, including oxygen therapy, CPAP, Non-Invasive Ventilation and vaccines (*as detailed in section 5.D*), since the last visit, if applicable,
- Occurrence of COPD exacerbations (*as defined in section 6.A.2.2*) since the last visit,
- Occurrence of other Adverse Events (*see section 6.B*) since the last visit,
- For patients on oxygen therapy, checking of the *NOWOX* device (*to detect the need for an exchange or return of the device at study end*), and, if applicable, the reason for exchanging or returning the *NOWOX* device and the serial number of the new *NOWOX* device assigned, whenever necessary; of note, patients starting oxygen therapy during their study participation will be given a *NOWOX* following the procedure described in section 4.B.3.1 and their start date and criteria for oxygen prescription will be collected, as described in section 4.B.1.2.
- Use of health care services (*see section 6.A.2.3*) since the last visit.

**At Visit 3 (Month 6) and Visit 5 (Month 12 or study end in case of premature withdrawal)**, additional questionnaires and examinations will be performed as follows:

- The SGRQ-C, 15D and HADS questionnaires (*as detailed in sections 6.A.2.4 and 6.A.2.7 and provided in Appendix 3*), self-administered before the consultation with the investigator at **Visit 3 (M6)** and **Visit 5 (M12)**,
- Assessment of the severity of dyspnoea using the modified Medical Research Council Dyspnoea Scale at **Visit 5 (M12)**,
- Comorbidities to allow the calculation of the Charlson Comorbidity Index at **Visit 5 (M12)**,

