### **PRIMARY ANALYSIS OF THE PRIMARY EFFICACY CRITERION**

The primary analysis of the primary efficacy criterion will correspond to the primary objective of the study, which is to evaluate a strategy of COPD management to reduce the average yearly duration of unscheduled hospitalisations whatever their reason, in patients with GOLD III/IV COPD.

In order to deal with patients followed-up over different duration, their individual recorded cumulated number of unscheduled hospital days whatever their reason ( $D_i$  expressed in days, as recorded by the investigators) will be normalised on a yearly basis, by multiplying  $D_i$  by the ratio [365 days / total number of days of the patient's *Follow-Up Period*] and rounding it at the nearest integer. Thus, a patient for whom 18 unscheduled hospital days have been recorded over a 6-month (182 days) follow-up prior to study premature withdrawal will be analysed as having experienced a yearly estimated duration of hospitalisation of [18 x (365/182)] ~ 36 days. In the same manner, a patient for whom 18 unscheduled hospital days have been recorded over a 2-year (731 days) follow-up will be analysed as having experienced a yearly estimated duration of hospitalisation of [18 x (365/731)] ~ 9 days.

On the ITT data set (*defined in section 7.B.3.1*), the normalised individual yearly duration of unscheduled hospitalisations whatever their reason will be considered as categorical data (0, 1, 2, 3, 4, ... days) and compared between the 2 study groups using the Wilcoxon's rank sum test, in all investigational centres and countries pooled together.

This non-parametric test is commonly used to test that the multinomial distributions of an ordinal categorical parameter are the same across 2 independent samples.

The null hypothesis of interest  $H_0$  is that the distribution of the normalised individual yearly duration of unscheduled hospitalisations whatever their reason in the Intervention group is equal to the one observed in the Control group. The alternative 2-sided hypothesis  $H_1$  is that the distribution of the normalised individual yearly duration of unscheduled hospitalisations whatever their reason in the Intervention group is different from the one observed in the Control group.

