### 8.B COLLECTION AND REPORTING OF SERIOUS ADVERSE EVENTS

The investigator is responsible for the detection and documentation of events meeting the definition of an AE or SAE as provided in this protocol. In order to fulfil the safety reporting obligations, the investigator should report all Serious Adverse Events occurring during the study, whether related to the study intervention or not, within 24 hours in the dedicated screen of the e-CRF, or when the e-CRF is not available, by fax or telephone to ITEC Services, for the attention of:

1. [name] [name], ITEC Services
2. [name], ITEC Services
3. [name], ITEC Services

[contact]

[contact]

A copy of the document to be filled in and faxed in case the e-CRF is not available will be provided in the investigator binder.

If ITEC Services cannot be reached, AIR LIQUIDE *Santé* INTERNATIONAL Pharmacovigilance department should be contacted:

Tel: [name]  
[contact]  
Email : [contact]

If the Pharmacovigilance Department cannot be reached, AIR LIQUIDE *Santé* INTERNATIONAL COMET study team at the Research and Development Centre Claude Delorme could be contacted:

Tel: [name]  
[contact]

The initial SAE declaration should include the following information: patient selection number, brief description of the event, its start date, and the reason(s) why the investigator considers the event serious.

The time period for the consideration and reporting of AEs (*either serious or not, according to their regulatory definition provided in section 8.A*) starts at the patient Selection (*i.e., at Visit 0*) and continues up to the last study visit (*i.e., up to Visit 5*).

The medical devices provided by AIR LIQUIDE *Santé* INTERNATIONAL for the study conduct are all CE marked and they are not under evaluation during the study. The investigators should thus follow the regular process for reporting any incidents and near-incidents related to those medical devices, whenever they occur throughout the study period.

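### The design sections end follow-up at Month 12 (Visit 5) for every patient, but the analysis sections follow the first patients to Month 24 (Visit 9), so the primary and safety windows are contradictory

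*Protocol*

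**What the plan says.** **Design text: one window for everyone.**
- Section 1.B: "the study primary objective is to show a significant reduction in the number of hospital days during the 12-month study follow-up".
- Section 3.A gives the planned duration as "including a 38-month enrolment period and a 14-month follow-up for each randomised patient".
- Section 4.B.3.2: the Follow-Up Period "starts at the end of Visit 1 and will last 12 months for each patient". Visits 2 to 5 "are scheduled at Month 3, Month 6, Month 9 and Month 12 from Visit 1, respectively".
- The flow chart in 6.E has no visit after Visit 5, and 3.D collects survival to Month 12.
- Section 8.B: adverse event reporting "continues up to the last study visit", which the parenthesis that follows identifies as Visit 5.

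**Analysis text: a second, 24-month cohort.**
- Section 7.B.3.5, primary analysis: the second worked example is a patient for whom "18 unscheduled hospital days have been recorded over a 2-year (731 days) follow-up".
- Section 7.B.3.5, compliance to oxygen therapy: up to eight between-visit periods, the last running from Visit 8 to Visit 9, for early patients followed 24 months.
- Section 7.B.3.7, extent of exposure: the last visit falls at Month 24 for the early patients and at Month 12 for the rest.
- Section 7.B.3.7, adverse events: the assessment window ends at "Visit 9 for the first patients included in the study or Visit 5 for the patients included afterwards".

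**The concern.** The primary criterion in 6.A.1 counts unscheduled hospital days during the Follow-Up Period, a term that 4.B.3.2 defines as 12 months. The formula in 7.B.3.5 divides by each patient's total follow-up, sets no limit at Month 12, and is illustrated with a denominator of 731 days. Under the protocol's own definition no patient can have that denominator. If such patients exist, their second-year days are averaged into the yearly value, and the quantity is no longer the 12-month one described in 1.B.

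Two other analyses have no adjustment at all. The numbers of moderate and severe exacerbations go to a Wilcoxon test as recorded, with no annualisation stated. The adverse event tables count patients with at least one event, a proportion that can only rise with time observed.

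The reporting rules also collide. Section 6.A.1 requires every hospitalisation to be reported as a serious adverse event. An admission at Month 18 would enter the primary value under the 7.B.3.5 formula, lie inside the 7.B.3.7 adverse event window, and lie outside the reporting period as 8.B specifies it.

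**Working it through.** **1. The plan's own figures reproduce.** Inputs from 7.B.2: difference 10 days, SD 25 days, two-sided alpha 0.05, power 0.90, and a 6.25% loss used for inflation.
- Noether formula for the rank-sum test: n per group = (1.960 + 1.282)² / [6(p − 0.5)²], with p = Φ(10 / (25√2)) = 0.6114. This gives 141.2, so 142. With p rounded to 0.611 it gives 142.1, so 143, as stated.
- 143 / (1 − 0.0625) = 152.5, so 153 per group and 306 in total, as stated.
- Worked normalisations: 18 × 365/182 = 36.1 and 18 × 365/731 = 8.99, matching the stated 36 and 9.

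The sample size is on a yearly scale and has no follow-up length as an input, so it is the same under either window.

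**2. Does a 731-day follow-up fit the stated participation?** Run-in is 5 weeks (35 days), exceptionally extended by 4 weeks (28 days). One month is taken as 30.44 days.
- 12-month window: (35 + 365)/30.44 = 13.1 months; with the extension, (35 + 28 + 365)/30.44 = 14.1 months. Both agree with the 14 months in 3.A.
- 731-day window: (35 + 731)/30.44 = 25.2 months. This cannot be reconciled with 14 months for each randomised patient.

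**3. What the second year would contain.** Section 4.B.3.2 schedules education sessions to Month 12 and has the devices, including NOWOX, collected at Visit 5. The oxygen analysis nevertheless expects NOWOX periods up to Visit 9. The protocol does not say what the early patients receive, or how they are observed, after Month 12.

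**4. Does mixing windows damage the primary test?** The protocol gives no share of 24-month patients, so this is illustrative only. Assumptions not in the documents: admissions are Poisson with gamma frailty (shape 0.8), stays average 12 days, mean days per year are 20 (control) and 10 (intervention), there are 143 patients per group, and the share on 24 months is the same in both arms. There were 2,000 replicates per scenario.

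Control group, annualised days:

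| Window | Mean | SD | Zero days | Median |
|---|---|---|---|---|
| 12 months | 20 | 30 | 41% | 7 |
| 24 months | 20 | 26 | 28% | 10 |

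Wilcoxon test by share of patients on 24 months:

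| Share | 0% | 10% | 25% | 50% |
|---|---|---|---|---|
| Type I error | 0.053 | 0.046 | 0.047 | 0.052 |
| Power | 0.90 | 0.90 | 0.91 | 0.93 |

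The Monte Carlo standard error at 0.05 is √(0.05 × 0.95/2000) = 0.005, so none of the type I error values differs detectably from 5%. Annualising equalises the mean but not the distribution that the test ranks. With the share equal in both arms, that changes what is estimated but not the validity of the test.

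**The case against.** The strongest reply is that unequal follow-up is a declared and handled choice. Section 7.B.3.5 annualises precisely because patients are observed for different durations, and it works both a short and a long case. With 25% yearly dropout expected in 7.B.2, lengths vary anyway, and a cut at Month 12 leaves the short follow-ups in place. Sections 7.B.2 and 7.B.3.5 word the objective as a yearly duration, and 2.A names no duration at all. This stands as a limit on the harm. It does not settle the window: annualising says how to scale the days, not which days count.

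A reader might infer that the mixture biases the comparison or inflates the type I error. The documents do not support that. The longer follow-up is assigned by order of inclusion, not by arm, patients are randomised within centre, and the simulation shows neither inflation nor loss of power. It does not test different second-year retention between arms, which nothing in the protocol quantifies.

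A reader might also infer serious damage to the safety and cost results. Section 7.B.3.7 performs no statistical test on safety, and an event with the same preferred term counts once per patient and period, so counts would not simply double. Costs are compared per month (7.B.3.6), and 6.C.2 and 6.C.3 already set cost-effectiveness and QALYs over 12 months.

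Section 8.B is partly open too: its main clause runs to the last study visit, and only the parenthesis naming Visit 5 conflicts with 7.B.3.7. Finally, one hospital day in 731 does round to zero (365/731 = 0.499), but that moves a single patient by one category and is trivial.

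**Conclusion.** The contradiction is real, stands in current text, and reaches the primary criterion. The design sections allow 12 months ending at Visit 5. Four places in the analysis sections use 24 months, 731 days or Visit 9, and nothing defines Visits 6 to 9 or says who or how many the early patients are. The defect is an inconsistent estimand and an inconsistent safety window, with exacerbation counts and adverse event percentages left uncorrected for unequal follow-up.

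It is not a sample size error, and no bias between arms or loss of type I error control has been shown. The effect on the result cannot be sized from the documents because the share of 24-month patients is not given; the 41% and 28% zero rates depend on assumed inputs. The 24-month wording may be a carry-over from an earlier follow-up scheme, but that is an inference. If it is, the analysis text is wrong; if a 24-month cohort exists, the design text is wrong. The point should be settled before database lock, because in an open trial an unsettled window could otherwise be chosen after results are seen.

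**What to change.** Before database lock:

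1. State in 6.A.1 and 7.B.3.5 that the primary criterion and the between-group efficacy comparisons, including exacerbation counts, use Visit 1 to Month 12, with annualisation of the primary value only for shorter follow-up. Say how this cut works with the ±30-day window around Visit 5.
2. Report any later data from the early patients separately and descriptively.
3. Present the adverse event tables for the same 12-month window.
4. Reconcile 3.A, 4.B.3.2, 6.E, 7.B.3.5, 7.B.3.7 and 8.B. Either remove the 731-day example and the Visit 9 and Month 24 text, or define the 24-month cohort, its visits and its adverse event reporting period.

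The cost is wording plus a date cut in the programs. Any second-year data leave the primary comparison, and a protocol amendment may be needed. The sample size stays at 306.

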## COPD EDUCATION

**Patients randomised in the Control group** will receive the usual COPD education as per investigational centre routine practice. The content and modalities of each centre will be collected before study initiation, as well as any modifications throughout the study period, if applicable.

**Patients randomised in the Intervention group** will undergo four (4) individual home education sessions, performed on a weekly basis by a community-based health professional (*called for the study 'health counsellor' and detailed in section 5.A.1*):

- The four sessions will be performed before Visit 1, in a minimum of 3 weeks and a maximum of 5 weeks after randomisation.
- Each individual session is planned to last 60 to 90 minutes during which the health counsellor will use specific teaching material in local study language and will give the patient the printed education documents (*handbooks and brochure, as detailed in section 5.A.1.1*) and the study medical devices (*portable pulse oximeter, spirometer and thermometer, as detailed in section 5.A.4*). The patient will also be trained to perform phone calls to the study dedicated vocal server. After each education session, the understanding and skills of the patient will be assessed and a report will be sent by the health counsellor to the investigator concerned.

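### The study emergent (SE) definition and the start-date period rule conflict, and anchoring SE at Visit 1 leaves Run-In events out of the intervention-associated AE count

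*Protocol*

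**What the plan says.** All of the rules stand under Adverse Events in protocol section 7.B.3.7. An AE reported after Visit 1 is SE in any of three cases: "if it begins after Visit 1 date"; "if its start date is unknown"; or "if it begins before Visit 1 and worsens at any time during the" Follow-Up Period. Two rules for incomplete records are added: "any AE starting before Visit 1 and going on afterwards will be considered study emergent if its severity is missing or partially filled in", and "any AE starting before Visit 1 with missing or incomplete end date will be considered study emergent".

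The period rule follows: "All reported AEs will be classified in these two (2) periods, according to their start date". The two periods are Run-In and Follow-Up.

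The main tables count patients with SE AEs in the Follow-Up Period, including by worst intensity and by relationship to the allocated intervention. A further requirement reads "Over both study periods, separately and globally, an additional summary table will be provided by study group". Its rows include patients with any SE AE and patients with any intervention-associated SE AE. A companion table counts SE AEs over the same periods, and both are repeated for serious AEs (SAEs).

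On the programme itself, section 4.B.3.1 (COPD Education) says of the Intervention group: "The four sessions will be performed before Visit 1". Section 4.B.1.2 has the written action plan handed over at Visit 0.

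**The concern.** The SE definition deliberately brings in events that did not start in Follow-Up, namely those that worsened and those with an unknown start. A period rule that looks only at the start date takes them out again. Two programmers following the same text could produce different Follow-Up tables, and both could claim to have followed the protocol.

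The second issue is the anchor. AE collection starts at Visit 0 (section 8.B), and so does the Intervention programme. An AE that the investigator links to the programme, and that starts and resolves before Visit 1, is not SE. It therefore cannot enter the intervention-associated count, for Run-In or overall. The rule is the same in both groups, but only one group receives the programme in that window. Safety is a stated secondary objective (section 2.B) and is reported without tests, so these descriptive counts are the safety result.

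**Working it through.** The protocol gives no figure to reproduce here; the check is one of logic. I applied the SE rules and the start-date rule of section 7.B.3.7 to eight AE patterns.

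| AE pattern | SE? | Period by start date | Consistent? |
|---|---|---|---|
| 1. Starts and resolves in Run-In, complete record | No | Run-In | Yes |
| 2. Starts in Run-In, worsens in Follow-Up | Yes | Run-In | Conflict |
| 3. Starts in Run-In, continues unchanged, complete record | No | Run-In | Yes |
| 4. Starts in Run-In, unchanged, end date missing | Yes | Run-In | Conflict |
| 5. Starts in Run-In, continues, severity missing | Yes | Run-In | Conflict |
| 6. Starts on the Visit 1 date | Not defined | Not settled by date alone | Undefined |
| 7. Start date unknown | Yes | None possible | Conflict |
| 8. Starts in Follow-Up | Yes | Follow-Up | Yes |

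Tally: 4 conflicts (patterns 2, 4, 5, 7) + 1 undefined (pattern 6) + 3 consistent (patterns 1, 3, 8) = 8.

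Three results follow.

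- **Follow-Up tables.** SE status combined with a Follow-Up start date leaves only pattern 8. The literal period rule therefore cancels the worsening and unknown-start rules for the main tables.
- **Run-In rows.** SE status combined with a Run-In start date leaves only patterns 2, 4 and 5: events that worsened later or have incomplete records. Pattern 1, the ordinary Run-In event, is excluded. The protocol confirms that reading. Where the same AE occurs once wholly within Run-In and again in Follow-Up, only the second occurrence is described as SE.
- **Visit 1 date.** The SE wording covers onset after that date and onset before Visit 1. Run-In ends when Visit 1 is completed and Follow-Up starts at that moment (sections 4.B.3.1 and 4.B.3.2), so a date without a time does not settle the period either.

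Pattern 4 depends on a term that the protocol does not define. If an AE still ongoing at study end counts as having a missing end date, an unchanged event becomes SE and the worsening condition is bypassed. If ongoing is recorded as a status of its own, it does not.

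**The case against.** The strongest reply is that Run-In events are not lost. Section 7.B.3.7 has safety data tabulated for Run-In on the Full Analysis Set (FAS) and for Follow-Up on the Intention To Treat (ITT) set. It also says that Run-In AEs will be tabulated on both sets in the format that follows, or only listed if few patients are affected. AEs leading to discontinuation or withdrawal are counted whatever their SE status. All SAEs from Selection are listed individually, and the SAE table by System Organ Class and preferred term, produced if relevant, carries no SE restriction. The rules are identical in both groups, and safety is descriptive. Treating incomplete records as emergent is a conservative convention, and anchoring SE at the start of Follow-Up is a legitimate design choice.

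Most of this stands, and it limits the point. A reader might infer that the AE and SAE tables by group are wrong. The text does not support that: table content is undetermined in places, and one count omits a class of events. Whether the SAE versions of the summary tables inherit the SE restriction is simply not stated.

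A reader might also infer that Run-In AEs are never emergent, or that every unchanged ongoing AE is. The first fails on patterns 2, 4 and 5. The second fails on pattern 3, and holds only if ongoing is equated with a missing end date, which the protocol does not do.

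What the reply does not remove is the conflict itself. The format to which the Run-In tabulation refers is written in terms of SE AEs, apart from the discontinuation and withdrawal rows. A non-serious, intervention-related AE that starts and resolves in Run-In, and leads to no discontinuation or withdrawal, has no clearly defined summary by relationship. These rules are stated in the protocol; they are not details left to the analysis plan.

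**Conclusion.** The concern holds in limited form. The SE definition and the start-date rule cannot both be applied as written to AEs that worsen after Visit 1 or have an unknown start, and onset on the Visit 1 date is not covered. The SE and intervention-associated SE rows required for Run-In and overall leave out AEs confined to Run-In, although the programme is already under way. Those AEs appear only in the Run-In tables or listings, apart from the discontinuation and withdrawal counts; SAEs also appear in the individual listing.

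The size is four of eight patterns in conflict and one undefined. That counts kinds of event, not events, and the protocol gives no AE rates from which to estimate a number. It is tempting to use Run-In's share of study time instead: 5/(5 + 52) = 8.8%, or 9/(9 + 52) = 14.8% with the exceptional four-week extension. That says nothing about how many events are affected. Nor does it fit the first patients, whom section 7.B.3.7 describes as followed to Month 24: 5/(5 + 104) = 4.6%.

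This is worth correcting before tables are programmed, at moderate-to-minor severity. It does not touch the primary analysis. The conclusion assumes that the period rule is meant literally; if it is not, the sentence still needs rewording.

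**What to change.** Reword section 7.B.3.7, and carry the same wording into the analysis plan:

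- For the Follow-Up SE tables, assign an AE that worsened to the period in which it worsened, and an AE with unknown start date to Follow-Up.
- Assign onset on the Visit 1 date to one stated period.
- State that an AE recorded as ongoing does not have a missing end date, and is SE only if it worsens.
- In the summary tables, count all AEs and SAEs, and all intervention-associated AEs and SAEs, from randomisation: Run-In on the FAS, Follow-Up on the ITT set. Keep the SE label for Follow-Up only. This also settles whether the SAE summaries are restricted to SE events.

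The cost is wording and some table reprogramming. Dates, severity and relationship are already recorded for every AE (section 6.B), from Visit 0 onwards (section 8.B), so no new data are needed. The small downside is that more events will enter the intervention-associated count.
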